## 7.3 Dose Modifications and Interruptions

### 7.3.1 Dose Escalation, Dose Reduction and Re-challenge

#### Dose Escalation

Patients will be categorised according to disease severity as determined by the presence or absence of clinically evident CVD, which will be defined by documented aortic valve disease or coronary atherosclerosis at Baseline.

Lomitapide will not be escalated, if LDL-C is less than the target threshold:

- LDL-C is <100 mg/dL (<2.5 mmol/L) in patients without CVD at Baseline
- LDL-C is <70 mg/dL (<1.8 mmol/L) in patients with CVD at Baseline

For each of the 3 age groups, lomitapide dosing will escalate following the applicable dose titration scheme in Table 2 at Week 4±3 days, Week 8±3 days, and Week 12±3 days to the maximum allowable dose by Week 16±3 days or the MTD by Week 20±3 days based upon acceptable safety and tolerability criteria in addition to LDL-C values.

Each dose must be tolerated for ≥4 consecutive weeks before being escalated to the next higher dose in stepwise increments. The MTD is defined as the highest dose of lomitapide through Week 24±3 days that does not result in tolerability or safety concerns. This is the highest dose that does not result in dose reduction, dosing interruption, or discontinuation, but may include a re-challenged dose level.

Each patient will continue receiving the MTD of lomitapide he/she achieved during the Efficacy Phase (unless criteria is met for reducing or increasing the dose) for an additional 80±1 weeks in the Safety Phase (for a total treatment period of 2 years).

If after Week 24±3 days both the investigator and the sponsor consider a patient 5 to 15 years of age to be eligible for further escalation of the lomitapide dose beyond the maximum recommended dose by the respective age group, the lomitapide dose can be increased to an extent defined by the investigator after consultation with the sponsor based on individual safety, efficacy, and concomitant LLT criteria. If the patient tolerates this new dose for ≥4 weeks, then this will be considered the new MTD.

If after Week 24±3 days, a patient has crossed over into the next age category, the study medication can be escalated to the maximum dose applicable for the new age category. If the patient tolerates this new dose for a minimum of 4 weeks, then this will be considered the new MTD.

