#### Dose Reduction and Re-challenge

If a dose reduction is required, dosage will either be reduced to the previous tolerated dose or to an intermediate dose. Please note that only down-titrations to intermediate doses are allowed, dose escalations need to follow the guidance provided in Table 2. After resolution of the cause for dose reduction, patients may be re-challenged after a minimum period of 4 weeks following dose reduction with prior doses in stepwise increments based on dose escalation guidelines, but may not exceed the MTD established during the Efficacy Phase until

Week 24±3 days, after which further increase is only possible if patients have crossed into the next age category or eligibility for exceptional dose escalation as described above is met.

If the investigator determines that a patient is not tolerating any particular dose (per specified criterion), the investigator may request a dose reduction or a hold on the current dose until the next scheduled visit. Once the patient has stabilised on the reduced dose, the dose can be increased back to the next step again, and the patient may progress through subsequent dose increases at a minimum of 4-week intervals. If the patient does not tolerate the re-challenge dose, then the MTD is considered the reduced dose and will be the highest dose allowed for the remainder of the study.

Weeks 0 through 24±3 days establish the MTD, Week 20±3 days is the last visit that the lomitapide dose can be increased, except when there has been a down-titration at/or after Week 16±3 days. Re-challenging will depend on the assessment of safety and tolerability criteria and the LDL-C value relative to the LDL-C goal of <135 mg/dL (3.5 mmol/L) and is at the discretion of the investigator except for Hy's law cases or comparable signs of liver toxicity, irrespective of origin, in which no re-challenge will be allowed (see Section 7.4 *Patient Discontinuation Criteria*).

The study medication can be escalated as a re-challenge dose during an unscheduled visit after the investigator consults with the study medical monitor, but any additional dose escalations, i.e., dose titration, must be made during a completed scheduled visit. In addition, a re-challenge with lomitapide will not be performed if the LDL-C is below the target threshold while the patient was receiving the reduced dose.

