### **HMG-CoA Reductase Inhibitors ('Statins')**

Lomitapide increases plasma concentrations of statins. Patients receiving lomitapide as adjunctive therapy to a statin should be monitored for AEs that are associated with the use of high doses of statins. Statins occasionally cause myopathy. In rare cases, myopathy may take the form of rhabdomyolysis with or without acute renal failure secondary to myoglobinuria, and can lead to fatality. All patients receiving lomitapide in addition to a statin should be advised of the potential increased risk of myopathy and told to report promptly any unexplained muscle pain, tenderness, or weakness (see Section 7.3.2 *Dose Modification, Interruption or Discontinuation for Adverse Events, Creatinine Kinase Monitoring and Evaluation*).

Concomitant administration of >40 mg simvastatin will not be permitted during the study as described in Section 7.6.3 Non-permitted Concomitant Medication, Food or Substances.

Since patients will be required to remain on their concomitant LLT (including LA, when applicable) established during the 6-week Run-in Period during the Efficacy Phase of the study through Week 24±3 days, a potential concomitant treatment with atorvastatin will remain unchanged during the Efficacy Phase, when lomitapide dosing will start. If atorvastatin is given concomitantly, it should be administered in the morning to separate it from lomitapide dosing by 12 hours. If during the 80-week Safety Phase it is not possible to administer atorvastatin and lomitapide 12 hours apart, the lomitapide dose should be reduced by half. After a minimum period of 4 weeks following dose reduction the patient can be re-challenged with a higher dose of lomitapide once these issues resolve (i.e., if atorvastatin can be administered 12 hours apart or if atorvastatin is discontinued), but the dose during the Safety Phase cannot exceed the MTD established during the Efficacy Phase unless eligibility for exceptional dose escalation is met (described in Section 7.3.1 *Dose Escalation, Dose Reduction and Re-challenge*).

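### For a child who enters an older age category after Week 24, the protocol permits escalation to the new maximum, yet after a failed re-challenge it also fixes the reduced dose as a ceiling to the end of the study, with no rule of precedence

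*Protocol*

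**What the plan says.** Four statements in the protocol bear on this child.

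- **Age-crossing permission.** Section 7.3.1 (Dose Escalation) says that after Week 24, for a patient now in the next age category, "the study medication can be escalated to the maximum dose applicable for the new age category". It continues: "If the patient tolerates this new dose for a minimum of 4 weeks, then this will be considered the new MTD". The synopsis (Section 1.1, Study design) and Section 4.2.1 carry the same permission.
- **Ceiling after a failed re-challenge.** Section 7.3.1 (Dose Reduction and Re-challenge) says that if the re-challenge dose is not tolerated, "then the MTD is considered the reduced dose and will be the highest dose allowed for the remainder of the study". The synopsis (Dosage and mode of administration) repeats this. Neither place states an exception.
- **Cap at the established MTD.** The same subsection says that after Week 24 "further increase is only possible if patients have crossed into the next age category or eligibility for exceptional dose escalation as described above is met", and the synopsis text below the dose-escalation table agrees. The closing paragraph of Section 7.3.1 caps the Safety Phase dose at the Efficacy Phase MTD and names exceptional escalation as the only exception. The synopsis (Study design) and Section 4.2.1 repeat that cap. Sections 2.6.3 and 7.3.3 apply it to re-challenge after an atorvastatin-related reduction, where the dose "cannot exceed the MTD established during the Efficacy Phase unless eligibility for exceptional dose escalation is met".
- **Stepwise rule.** Section 7.3.1 says "Each dose must be tolerated for ≥4 consecutive weeks before being escalated to the next higher dose in stepwise increments", and in the re-challenge subsection that "dose escalations need to follow the guidance provided in Table 2".

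**The concern.** A child who failed a re-challenge and later has an eleventh or sixteenth birthday falls under both the permission and the ceiling. Two sites could follow the protocol faithfully and treat the same child under different dose limits. These are children already shown not to tolerate a higher dose, so this is first a safety matter.

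It also affects interpretation. Lipid changes, liver fat and adverse events after Week 24 are summarised as results of one dosing scheme, and safety is also shown by age group (Section 12.3.6). If sites resolve the conflict differently, the Safety Phase dose partly reflects which sentence was read. The analysis plan cannot repair that afterwards.

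**Working it through.** The protocol states no figure on this point to reproduce. The check sets the passages side by side, with a small count of dose steps and of children.

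**1. Permission against the failed-re-challenge ceiling**

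- Permission: it applies to any patient who has crossed an age boundary after Week 24. Its limit is the new category's maximum. Patients whose MTD was set by intolerance are not excluded.
- Ceiling: it applies to any patient who failed a re-challenge. Its limit is the reduced dose, and it lasts to the end of the study. Age crossing is not excepted.
- Example: a 10-year-old is reduced from 10 mg to 5 mg, fails re-challenge at 10 mg, and turns 11 in the Safety Phase. The ceiling gives a limit of 5 mg. The permission gives a limit of 40 mg (Table 2, 11 to 15 years).
- Both conditions are met, the limits differ, and no order of precedence is stated.

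**2. Safety Phase cap against the age-crossing route**

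- The re-challenge subsection and the synopsis list two routes above the established MTD, joined by 'or': age crossing and exceptional escalation.
- The two differ in substance. Exceptional escalation needs the agreement of investigator and sponsor and is limited to patients aged 5 to 15 years. The age-crossing sentence asks for neither.
- The closing paragraph of Section 7.3.1 and its repeats name only exceptional escalation. Read literally, they bar what the re-challenge subsection allows.

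**3. Whether the steps apply**

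Table 2 doses (mg) are 2, 5, 10, 20 for ages 5 to 10; 2, 5, 10, 20, 40 for ages 11 to 15; and 5, 10, 20, 40, 60 for ages 16 to ≤17. Steps from the current dose to the new maximum:

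| Crossing | From 2 mg | From 5 mg | From 10 mg | From 20 mg | From 40 mg |
|---|---|---|---|---|---|
| 5–10 to 11–15 (40 mg) | 4 | 3 | 2 | 1 | – |
| 11–15 to 16–≤17 (60 mg) | 5 | 4 | 3 | 2 | 1 |

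A child at the old maximum (20 or 40 mg) is one step from the new one, so the question does not arise. For a child below it, a direct move would pass over (steps − 1) intermediate doses, that is 1 to 4 doses. At 4 weeks per dose this is 4 × 1 = 4 to 4 × 4 = 16 weeks of required tolerance.

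**4. How many children could cross a boundary**

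Assumptions: ages spread evenly within each band and 15 enrolled per group (45/3). The oldest group has no higher category.

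- Treatment time: 104 weeks = 104 × 7/365.25 = 1.99 years.
- Ages 5 to 10 (6 years wide): 1.99/6 = 33%; 15 × 0.33 ≈ 5.
- Ages 11 to 15 (5 years wide): 1.99/5 = 40%; 15 × 0.40 ≈ 6.
- Total: about 11 of the 30 children in the two younger groups, before dropout.
- If the planned loss by Week 24 (30 of 45 remaining) is unrelated to age: 11 × 30/45 ≈ 7.

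These figures count everyone who crosses. The hard conflict needs a failed re-challenge as well, and the protocol gives no rate for that.

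**The case against.** The strongest defence is that a specific restriction limits a general permission. The ceiling is explicit and the permission says only 'can', so the two could be read together as needing no more than a cross-reference. That is a reasonable reading, but the text does not state it. The opposite reading is also open: the paragraph just before the ceiling names age crossing as a route to a higher dose after Week 24.

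Other parts of the defence stand and limit the point:

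- **The established-MTD cap.** A reader might infer that the protocol forbids any age-crossing increase above the MTD. It does not: the re-challenge subsection and the synopsis expressly allow one. The contrary Safety Phase sentence is about re-challenge after a reduction, and Sections 2.6.3 and 7.3.3 apply it to atorvastatin-related reductions. In the synopsis and Section 4.2.1 its back-reference follows the age-crossing bullet and could be taken to include it. This conflict is therefore softer.
- **The stepwise rule.** A reader might infer that the age-crossing sentence drops the steps and allows a direct jump, for example 8-fold from 5 to 40 mg. The documents do not support this. The stepwise and Table 2 rules are general and nowhere waived, and Sections 4.2.1 and 7.2 speak of escalation to the maximum for the ordinary titration too, which is stepwise. The sentence is ambiguous because it names only the end dose and one tolerance period.
- **Liver monitoring.** A reader might infer that a new MTD set after Week 56 would have no scheduled liver test behind it, because visits are then 12 weeks apart. But 4 weeks is a minimum, the next scheduled visit includes liver tests, and Section 2.6.3 requires aminotransferases before each escalation. Asking for a named laboratory result would add a clinical requirement.
- **Reach.** Escalation is barred below the LDL-C thresholds, and the age-crossing route opens only after Week 24.

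**Conclusion.** The protocol is wrong as written on one point, inconsistent on a second and unclear on a third.

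- **Wrong:** the age-crossing permission and the failed-re-challenge ceiling give opposite answers for a child who meets both, and nothing ranks them.
- **Inconsistent, but softer:** the Safety Phase cap omits the age-crossing route that the re-challenge subsection names.
- **Unclear:** whether the stepwise rule governs an age-crossing increase, for children whose MTD is below the old category's maximum.

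The number of children in the hard conflict is unknown. A reader might take 11 of 30 as the number affected. That figure counts all who might cross a boundary, under an assumed even age spread and before dropout, and the affected group is a subset of it. The primary endpoint and the tested Week 24 hierarchy are untouched. What is at stake is the safety of children with a demonstrated intolerance, and a consistent dosing rule behind the later Safety Phase results. I take no view on which limit is clinically right.

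**What to change.** Reconcile the following into one rule with identical wording: the synopsis (Study design; Dose escalation by age group; Dosage and mode of administration), Section 4.2.1, all of Section 7.3.1, and the repeats of the cap in Sections 2.6.3 and 7.3.3. The rule should state:

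1. whether the ceiling after a failed re-challenge still binds once a child has crossed an age boundary;
2. whether the Safety Phase cap binds after an age crossing, naming or excluding that route in every place where the cap is repeated;
3. whether an age-crossing increase follows the stepwise and Table 2 rules.

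The choice of rule is the sponsor's. The cost is amendment wording and a training note to sites, with no added patients or procedures.

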#### Dose Reduction and Re-challenge

If a dose reduction is required, dosage will either be reduced to the previous tolerated dose or to an intermediate dose. Please note that only down-titrations to intermediate doses are allowed, dose escalations need to follow the guidance provided in Table 2. After resolution of the cause for dose reduction, patients may be re-challenged after a minimum period of 4 weeks following dose reduction with prior doses in stepwise increments based on dose escalation guidelines, but may not exceed the MTD established during the Efficacy Phase until

Week 24±3 days, after which further increase is only possible if patients have crossed into the next age category or eligibility for exceptional dose escalation as described above is met.

If the investigator determines that a patient is not tolerating any particular dose (per specified criterion), the investigator may request a dose reduction or a hold on the current dose until the next scheduled visit. Once the patient has stabilised on the reduced dose, the dose can be increased back to the next step again, and the patient may progress through subsequent dose increases at a minimum of 4-week intervals. If the patient does not tolerate the re-challenge dose, then the MTD is considered the reduced dose and will be the highest dose allowed for the remainder of the study.

Weeks 0 through 24±3 days establish the MTD, Week 20±3 days is the last visit that the lomitapide dose can be increased, except when there has been a down-titration at/or after Week 16±3 days. Re-challenging will depend on the assessment of safety and tolerability criteria and the LDL-C value relative to the LDL-C goal of <135 mg/dL (3.5 mmol/L) and is at the discretion of the investigator except for Hy's law cases or comparable signs of liver toxicity, irrespective of origin, in which no re-challenge will be allowed (see Section 7.4 *Patient Discontinuation Criteria*).

The study medication can be escalated as a re-challenge dose during an unscheduled visit after the investigator consults with the study medical monitor, but any additional dose escalations, i.e., dose titration, must be made during a completed scheduled visit. In addition, a re-challenge with lomitapide will not be performed if the LDL-C is below the target threshold while the patient was receiving the reduced dose.

During the 80-week Safety Phase, the lomitapide dose can be reduced from the MTD due to tolerability or safety issues, and the patient can be re-challenged with a higher dose of lomitapide once these issues resolve (after a minimum period of 4 weeks following dose reduction), but the dose during the Safety Phase cannot exceed the MTD established during the Efficacy Phase unless eligibility for exceptional dose escalation described above is met.

Please refer to Section 7.3.2 *Dose Modification and Interruption for Adverse Events* for further details regarding dose reductions due to AEs and to Section 7.3.3 *Dose Modification for Concomitant Medication* for detailed information about dose reductions depending on concomitant medication.

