### **7.3.2 Dose Modification, Interruption or Discontinuation for Adverse Events**

The investigator and/or DSMB have the authority to reduce study medication dosage or discontinue study medication in a patient if situations develop that, in the opinion of the investigator or DSMB, would compromise the patient's safety or successful participation in the study (see Section 4.3 *Data Safety Monitoring Board* and Section 7.4 *Patient Discontinuation Criteria*). In particular, modifications in dosage or discontinuation of treatment will be instituted if any of the situations below apply.

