#### Level 3 Hepatotoxicity

Level 3 Hepatotoxicity is defined as follows:

- Patients who experience ALT or AST  $\geq 5 \times$  ULN on 2 separate occasions and at least 7 days apart.

Patients who experience confirmed Level 3 Hepatotoxicity will immediately interrupt study medication. The patient will return to the clinic for repeat blood tests including AP, bilirubin and International normalised ratio (INR) every 7 days until the aminotransferase levels have fallen  $< 3 \times$  ULN. Once this occurs, study drug dosing may be resumed at the dose level below that associated with Level 3 Hepatotoxicity.

If this dose level is tolerated without elevation of ALT or AST  $> 3 \times$  ULN, then this dose will be defined as the MTD. If aminotransferases increase  $\geq 3 \times$  ULN further dose reduction or interruption may be necessary consistent with the guidance provided in this protocol.

Elevations in ALT or AST  $> 3 \times$  ULN that persist despite dose reduction or interruption for  $\geq 4$  weeks will be reported to the DSMB by the sponsor (or its designee) immediately upon notification. Patients will be referred to a hepatologist for further work up.

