### Level 2 Hepatotoxicity

Level 2 Hepatotoxicity is defined as follows:

- Patients who experience ALT or AST 3.0 to 4.9 x ULN on 2 separate occasions and at least 7 days apart.

Patients who experience confirmed Level 2 Hepatotoxicity will have the dose of study medication reduced to the previous tolerated dose. The patient will return to the clinic for repeat blood tests including AP, bilirubin and INR every 7 days until the aminotransferase levels have fallen to <3 x ULN. Once this occurs, lomitapide dosing may be resumed at the dose level below that associated with Level 2 Hepatotoxicity.

If this dose level is tolerated without elevation of ALT or AST >3 x ULN, then this dose will be defined as the MTD. If aminotransferases increase >3 x ULN further dose reduction or interruption may be necessary consistent with the guidance provided in this protocol.

Elevations in ALT or AST >3 x ULN that persist despite dose interruption for  $\geq 4$  weeks will be reported to the DSMB by the sponsor (or its designee) immediately upon notification. Patients will be referred to a hepatologist for further work up.

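### In the Safety Phase, Sections 7.3.1 and 7.3.2 give a child with confirmed Level 2 or 3 hepatotoxicity two different dose ceilings, and neither is said to govern

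*Protocol*

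**What the plan says.** Section 7.3.2 sets the liver rules. After confirmed Level 2 hepatotoxicity the dose is lowered, and "If this dose level is tolerated without elevation of ALT or AST >3 x ULN, then this dose will be defined as the MTD". After Level 3, dosing is interrupted, may resume one level lower, and if tolerated "then this dose will be defined as the MTD". Neither rule is limited to a study phase and neither describes a return to the earlier dose. The section opens by making its actions mandatory: "modifications in dosage or discontinuation of treatment will be instituted if any of the situations below apply".

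Section 7.3.1 sets the re-challenge rules. In general, "patients may be re-challenged after a minimum period of 4 weeks following dose reduction with prior doses in stepwise increments", once the cause has resolved and subject to a cap at the Efficacy Phase MTD. A reduced dose becomes the ceiling only after a failed attempt: "If the patient does not tolerate the re-challenge dose, then the MTD is considered the reduced dose". For the Safety Phase, after a reduction for tolerability or safety, "the patient can be re-challenged with a higher dose of lomitapide once these issues resolve (after a minimum period of 4 weeks" have passed since the reduction. The limit is that "the dose during the Safety Phase cannot exceed the MTD established during the Efficacy Phase", apart from exceptional escalation. The synopsis (Study design) and Section 4.2.1 repeat this Safety Phase rule.

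The only liver exception to re-challenge in Section 7.3.1 is a Hy's law case or comparable toxicity. Its pointer to Section 7.3.2 concerns dose reductions for adverse events. It does not mention re-challenge.

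**The concern.** A child who has a confirmed ALT or AST elevation in the Safety Phase falls under both sections. One names the lower dose as the MTD. The other allows a return to any dose up to the Efficacy Phase MTD, and that may be the dose on which the elevation occurred. Two sites could treat identical children differently, and both could claim to follow the protocol.

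The level of oversight is also uneven. Resuming after Level 4 requires the investigator, the DSMB and the sponsor to agree that benefit justifies the risk. Returning to the triggering dose after Level 2 or 3, at a scheduled visit, needs only the investigator's judgement. At stake are hepatic safety and consistent dosing in children. The primary test is not at stake.

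**Working it through.** **1. The two rules side by side, Safety Phase**

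| | Section 7.3.2 | Section 7.3.1 |
|---|---|---|
| Trigger | Confirmed Level 2 or 3 | Any reduction for tolerability or safety |
| Status of the lower dose | MTD, if tolerated without ALT/AST >3 x ULN | MTD only after a failed re-challenge |
| Return to the earlier dose | Not mentioned | Allowed after at least 4 weeks, once resolved |
| Ceiling | The lower dose | The Efficacy Phase MTD |

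**2. Worked path** (Table 2, age 11 to 15, Efficacy Phase MTD 40 mg)

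- ALT is 3.5 x ULN at the Week 32 visit. It is confirmed 7 days later, at Week 33, and the dose drops to 20 mg, which is tolerated.
- Section 7.3.2: the MTD is 20 mg.
- Section 7.3.1: re-challenge at 40 mg is open from 33 + 4 = Week 37 at an unscheduled visit after consulting the medical monitor, or at the Week 40 scheduled visit. The synopsis mentions only the next scheduled visit.
- Possible time at the higher dose to Week 104: 104 − 40 = 64 weeks, or 104 − 37 = 67 weeks. This is a difference in exposure. It would be reached only by a child who then tolerates 40 mg.

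**3. Size of one dose step** (Table 2, upward ratios)

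- Age 5 to 10: 5/2 = 2.5, 10/5 = 2, 20/10 = 2.
- Age 11 to 15: 2.5, 2, 2, 40/20 = 2.
- Age 16 to 17: 2, 2, 2, 60/40 = 1.5.

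One step is therefore 1.5- to 2.5-fold.

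**4. Efficacy Phase**

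If Section 7.3.2 has already made the lower dose the MTD, the cap in Section 7.3.1 blocks the earlier dose and the sections largely agree. Some ambiguity is left. The MTD definition reads "This is the highest dose that does not result in dose reduction, dosing interruption, or discontinuation, but may include a re-challenged dose level", and Section 7.3.1 lowers the MTD only after a failed re-challenge.

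Timing narrows this further. On scheduled liver tests, the earliest re-challenge is the first test on the dose, plus 1 week to confirm, plus 4 weeks.

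| Dose started | First liver test | Earliest re-challenge |
|---|---|---|
| Week 8 | Week 12 | Week 17 (scheduled visit Week 20) |
| Week 12 | Week 16 | Week 21 (unscheduled only, before Week 24) |
| Week 16 (top step) | Week 20 | Week 25 (after the Week 24 ± 3 day window) |

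**5. How many children**

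Section 2.6.3 reports ALT and/or AST >3 x ULN at least once in 10 of 29 adults: 10/29 = 34% (exact 95% CI 18% to 54%). Section 12.1.2 plans 45 enrolled and 30 evaluable at Week 24. Assuming the adult rate carries over, 30 × 10/29 = 10.3, or about 10 (30 × 0.179 = 5 to 30 × 0.543 = 16). The adult count covers single, unconfirmed elevations over the whole adult study. Requiring a second reading at least 7 days later and onset after Week 24 lowers it.

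**The case against.** The strongest reply is that the sections do not strictly contradict each other. Section 7.3.2 never forbids re-challenge, Section 7.3.1 only permits it, and a site that stays at the lower dose satisfies both. Section 7.3.2 is also the specific, mandatory rule, and Section 7.3.1 points to it straight after the Safety Phase paragraph. This has weight, but it does not close the gap. The pointer covers reductions only, and no text gives one section precedence. A dose named as the maximum tolerated dose means little if a higher one may follow at discretion.

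The point about harm largely stands. Re-challenge requires resolution, at least 4 weeks, and LDL-C not below the target threshold. Section 2.6.3 calls for aminotransferase checks before each escalation. After re-challenge Section 7.3.2 applies again, and a failed attempt fixes the lower dose for the rest of the study. The 12-week visit interval after Week 56 applies to every patient and does not come from this wording.

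Three stronger readings are tempting:

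- A reader might infer that Level 3 already counts as liver toxicity comparable to Hy's law, so that re-challenge is barred. That exception goes with permanent discontinuation, whereas Levels 2 and 3 expressly allow continued dosing.
- A reader might infer an equal conflict in the Efficacy Phase, with the Week 24 result at risk. The Efficacy Phase cap and the timing above do not support that.
- A reader might apply the adult rate to all 45 enrolled (45 × 10/29, about 16). That is not a Safety Phase count.

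**Conclusion.** The concern holds for the Safety Phase. The protocol states two ceilings for the same child and does not say which governs. The consequence is inconsistent dosing between sites by one Table 2 step, and possible re-exposure to the triggering dose on the investigator's judgement alone. In the Efficacy Phase only a residual ambiguity is left.

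At the adult rate, about 10 of some 30 children is a generous figure for those affected. It rests on adult elevations carrying over to children and on about 30 children entering the Safety Phase. Existing monitoring limits the likely harm. No sample size, power or alpha figure changes. It is worth correcting because it is a dosing rule for children on a drug with known hepatic effects, and the correction is cheap.

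**What to change.** 1. In the Safety Phase paragraph of Section 7.3.1, and where it is repeated in Section 4.2.1 and the synopsis (Study design), replace the cap with: *cannot exceed the current MTD, including an MTD redefined under Section 7.3.2*. Sections 2.6.3 and 7.3.3 repeat the same cap for atorvastatin and should be aligned.
2. Add to Section 7.3.1 and to the dosage part of the synopsis: *After confirmed Level 2 or Level 3 Hepatotoxicity, Section 7.3.2 governs: the lower tolerated dose is the MTD, and any later increase above it (re-challenge after a removable cause, age-category crossing, or exceptional escalation) needs normalised transaminases and medical-monitor or DSMB agreement.*
3. Leave the Level 4 rule as it is.

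This keeps the age-crossing and sponsor-agreed increases that Section 7.3.1 allows. It also keeps a route back after a removable cause. Section 2.6.3 describes such reintroduction in the adult extension study, after events linked to CYP 3A4 inhibitors or alcohol.

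The cost is a few lines in the next amendment and a note to sites. No new data, visits or patients are needed. The downside is that a few children with a reversible cause wait for the agreement before going back up.
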